Purpose: This study will examine the clinical success of 3 composite resins, a conventional composite (Filtek Supreme Ultra Universal Restorative, 3M ESPE) placed in 2 mm increments, a flowable composite resin (3M ESPE, Filtek Supreme Ultra Flowable, a flowable composite placed in 2mm increments) and a bulk placed and cured composite (Filtek Bulk Fill Flowable Restorative, 3M ESPE). All composite resin restorations will be placed using a single adhesive Scotchbond Universal in a three year clinical trial.

Objective: The objective of this study is to evaluate the clinical efficacy of these three restorative materials placed in class II posterior restorations using Scotchbond Universal adhesive. To accomplish this goal we will place 50 class II composite resin restorations for each material and evaluate them in accordance with the ADA and FDI criteria.

Specific Aims

1. Place and 50 composite resins of each composite in Class II cavity preparations, evaluate the resin composite restorations used in the three techniques at baseline, 6 months, 1 year, 2 years, and 3 years, using specific criteria (Attachment 2).
- 2.

Specific Aim: To place three commercially available resin composites in Class II cavity preparations, evaluate the resin composite restorations at baseline, 6 months, 1 year, 2 and 3 years using specific criteria (direct and indirect).

Materials:

Filtek Supreme Ultra Universal, 3M ESPE, placed and cured in 2 mm increments, Filtek Supreme Ultra Flowable a flowable composite resin placed and cured in 2 mm increments, and Filtek Bulk Fill Flowable a composite placed and cured in 4 mm increments will be used in this study. All restorations will be placed with an adhesive, Scotchbond Universal, using a total etch technique. **All composites and the adhesive used in this study are in use in the US dental market at this time and are commercially available (3M ESPE website).**

Duration of the Investigation:

36 months

Number of Restorations:

At least 40 restorations are needed at 36-month recall. Our experience at the UAB – School of Dentistry Clinical Research area with dropouts over a 36-month period is about 10%. Fifty restorations will be placed to ensure ample restorations at the 36-month recall.

Class of Restorations:

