Restorations will be placed in separate preparations in Class II in upper and lower jaw molars. All teeth will have natural teeth or crown and bridgework as antagonists. For the clinical evaluation of the resin, specific criteria (Attachment 2) will be used to evaluate, directly and indirectly.

Distribution of Restorations:

Sets of three restorations, one of each composite will be placed per patient for evaluation. If needed by the subject two sets of class restorations may be placed.

Patient Population:

Patients for this investigation will be selected from patients of the Dental School at the University of Alabama at Birmingham (UAB) and from those recruited from advertisements placed in newspaper ads. Approximately 50 subjects ranging in age from 19 to 90 years will be recruited for this study. The estimated subject number depends upon the number of restorations placed per subject. Pregnant women will not be included in this study.

Inclusion Criteria:

- must have given written informed consent to participate in the trial
- must need at least three posterior dental fillings
- replacement restorations due to caries or an esthetic replacement with or without caries are acceptable.
- must be available for the required post-operative follow-up visits
- restorations must be in contact with opposing natural or crowned teeth with at least one occlusal contact in habitual closure
- Class II restorations must have at least one proximal contact
- all restorations must be Class II with a proximal contact with a natural or artificial tooth

Subjects may be excluded from this study if they:

- have severe medical complications (organ transplants, long term antibiotic or steroid treatment, cancer or immunocompromised) and disabilities who may not be able to tolerate the time required to complete the restorations or to provide adequate oral hygiene
- have xerostomia either by taking medications known to produce xerostomia or those with radiation induced or Sjogren's syndrome patients
- have chronic periodontitis, rampant caries or poor oral hygiene which may require extraction of the teeth to be restored
- are unavailable for long term recall
- cannot tolerate the rubber dam required for isolation of the tooth during preparation and restoration.
- do not meet all inclusion criteria
- present with any systemic or local disorders that contra-indicate the dental procedures included in this study
- have an unstable occlusion

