The categorized clinical assessment data (color, marginal discoloration, secondary caries, anatomic form, marginal adaptation) will be summarized by computing percentages for each category and used to describe trends noted in the performance of the groups. In the analysis of categorical data of staining, marginal integrity, proximal contact, recurrent caries, retention, anatomical form and marginal adaptation, the frequency distribution over various categories will be calculated and reported. A sample size of 50 restorations is not based on a statistical plan, but rather on guidelines put forth by the American Dental Association for obtaining approval as an amalgam replacement for posterior restorations. The guidelines specifically call for an evaluation of a minimum of 40 restorations in a minimum of 20 subjects at 18 months. The basis for sample size is based by taking subject attrition into account over the 36 month clinical evaluation. All enrolled subjects, defined as those who have at least one experimental composite resin restoration - will be evaluated for safety of the composite.

Restoration survival at thirty-six months will be assessed using Kaplan-Meier survival analysis and Log Rank (Mantel-Cox) test for equality. The three groups will be compared with Kruskal-Wallis H test (mean rank scores, chi-square values, degrees of freedom, and p-values) for each FDI criteria at the thirty-six month recall using SPSS software (Microsoft).

Criteria for evaluation:

Modified USPHA and FDI criteria will be used to assess individual restorations. Silicone impressions will be made at each recall to measure the marginal integrity and loss of anatomical form of each restoration.

SUMMARY

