Subjects that are from 19-90 years old will be eligible for this study. Patients with health problems, who cannot tolerate the dental appointment, will be excluded. Signs advertising the study will be posted in the dental school and in the local newspaper. Up to 2 sets of three dental fillings for each patient will be filled with these materials in moderate sized cavities. The patient's teeth will be restored by using a local anesthetic and a rubber sheet (rubber dam) placed over the prepared teeth to isolate the cavities from the patient's saliva. The cavities will be prepared using currently accepted procedures, an impression or digital scan made of the preparation and the resin composite filling material will be placed after applying an etchant and adhesive to the cavity. The filling materials will be placed in increments according to the instructions for use. To ensure that the material is set or hardened sufficiently, the curing light (Elipar Deep Cure S, 3M ESPE) that activates the polymerization reactions of the filling material. The light will be routinely checked to verify it meets the curing specifications noted in the composite instructions for use. The biting surface of the restoration will be adjusted so that the patient's teeth function the same as before the procedure. The restoration will be polished and an impression and digital scan of the completed filling will be made to record the filling at that point with and without occlusal biting markings. A trained dentist will examine the patient's fillings at 1 week, 6 months, 1, 2, and 3 years after placement of the filling. At each recall appointment, discoloration and decay at the margin of the restoration, wear of the biting surface, presence of defects such as gaps at the margin, amount of contact between adjacent teeth, and color matching with natural teeth will be recorded as scores according to an accepted clinical rating system. For each category in the evaluation, percentages of alpha (perfect) scores will be tabulated. Video images of the procedure to document the filling placement for at least one patient will be made

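### The three materials are compared within patients by design, but the planned Kruskal-Wallis and log-rank tests treat them as independent groups and so probably lose some power

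*Combined protocol and SAP*

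**What the plan says.** The design is a matched one. Distribution of Restorations states: "Sets of three restorations, one of each composite will be placed per patient for evaluation". It then allows a second set: "If needed by the subject two sets of class restorations may be placed". The SUMMARY agrees: "Up to 2 sets of three dental fillings for each patient will be filled with these materials in moderate sized cavities".

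On numbers, the Objective says "we will place 50 class II composite resin restorations for each material", and Patient Population says "Approximately 50 subjects ranging in age from 19 to 90 years will be recruited for this study". Together these give about one set per patient. The split is not fixed, however: "The estimated subject number depends upon the number of restorations placed per subject". If every patient had two sets, 50 / 2 = 25 subjects would be enough.

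On analysis, the Data Analysis section says of the scores at 36 months: "The three groups will be compared with Kruskal-Wallis H test", applied to each FDI criterion. Restoration survival is shown by Kaplan-Meier curves and compared by a log-rank test. Neither that section nor any other mentions blocking, stratification by patient, clustering or a patient effect.

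**The concern.** Kruskal-Wallis and the unstratified log-rank test take their null variance from independent groups. Here the groups share their patients. Oral hygiene, diet, bite and caries activity belong to the patient, so restorations in one mouth may resemble each other whatever the material. When every patient contributes equally to all three materials, that shared part cancels from the comparison of materials but stays in the variance that Kruskal-Wallis uses. The p-values are then too large.

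The trial is a head-to-head comparison, and these are its only stated between-group tests. A conservative test makes a non-significant result more likely, and that result could be read as showing that the materials perform alike.

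The opposite error is also possible. If many patients had two sets, and two restorations of the same material in one patient were more alike than two of different materials, Kruskal-Wallis could reject too often.

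**Working it through.** **Inputs from the protocol.** 50 restorations per material; about 50 subjects; one set per patient, two at most; about 10% dropout over 36 months (Number of Restorations). This leaves 50 × 0.9 = 45 sets. The plan's 50 is not the result of a formula: 40 / 0.9 = 44.4, so 45 would keep the required 40, and 50 allows for a 20% loss. No power or alpha is stated, so there is no planned operating characteristic to reproduce.

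**Assumed inputs.** Nominal 5% tests; latent normal scores cut into three grades; one material shifted; within-patient latent correlation 0 to 0.5; three score distributions from 70/22/8% to 95/4/1%.

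**Why the direction is conservative.** Rank all restorations together. Let T_j be the rank sum of material j over n one-set patients, S² the variance of all ranks, and s_i² the variance of the three ranks within patient i.

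- Kruskal-Wallis: H = Σ(T_j − T̄)² / (n·S²)
- Patient-blocked rank test: Q = Σ(T_j − T̄)² / Σs_i²

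The numerators are identical, so H = Q × (mean s_i² / S²) ≈ Q × (1 − r), where r is the within-patient rank correlation. Under the null Q is approximately chi-square with 2 df, critical value 5.991. The true size of Kruskal-Wallis is therefore about exp(−2.996 / (1 − r)). For 70/22/8% scores, latent correlations of 0.1, 0.2, 0.3 and 0.5 correspond to r = 0.063, 0.129, 0.197 and 0.347. At 0.3, exp(−2.996 / 0.803) = 2.4%. The four sizes are 4.1, 3.2, 2.4 and 1.0%, close to the simulated 3.9, 3.4, 2.6 and 1.0%.

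**Simulated power, 45 one-set patients, shift 0.6 SD** (Kruskal-Wallis vs blocked, %; 10,000 runs per power figure, 20,000 per size figure):

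| Latent correlation | 70/22/8% | 90/8/2% | 95/4/1% | Kruskal-Wallis size, 70/22/8% |
|---|---|---|---|---|
| 0 | 69 vs 68 | 51 vs 50 | 37 vs 37 | 4.8% |
| 0.1 | 68 vs 71 | 50 vs 52 | 38 vs 39 | 3.9% |
| 0.2 | 70 vs 75 | 50 vs 54 | 37 vs 39 | 3.4% |
| 0.3 | 71 vs 80 | 50 vs 57 | 36 vs 41 | 2.6% |
| 0.5 | 71 vs 88 | 49 vs 65 | 35 vs 46 | 1.0% |

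The blocked test keeps a size of 4.6 to 4.9% for 70/22/8%. Over shifts of 0.4, 0.6 and 0.8 SD and all three distributions, the loss is 1 to 2.5 points at 0.1, 2 to 6 at 0.2 and 3 to 10 at 0.3. At 0.5, an upper sensitivity value only, it is 3 to 21. A separate simulation with 60/30/10% and 80/15/5% scores gave the same pattern.

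**A few two-set patients** (41 patients, 4 with two sets, 70/22/8%, 0.6 SD): 69 vs 71, 70 vs 75 and 70 vs 79 at 0.1, 0.2 and 0.3. With 5% of restorations missing: 67 vs 67, 67 vs 71 and 67 vs 75.

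**The liberal case.** With a patient-by-material share of the variance of 0.1, 0.2 or 0.3 and shared correlation 0.1, the size of Kruskal-Wallis is:

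- 4 of 41 patients with two sets: 4.5, 4.2, 4.6%
- 10 of 35: 4.5, 4.7, 5.2%
- 22 of 23: 4.8, 5.9, 7.2%

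At shared correlation 0 and share 0.3 the three layouts give 5.1, 6.4 and 8.0%. A test that permutes material labels at patient level stays at 4.4 to 5.0% in these runs.

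**Survival, one set per patient, correlation 0.3** (plain vs patient-stratified log-rank, one material worse): 39 vs 44 for 2% against 10% failures, 68 vs 71 for 5% against 20%, and 85 vs 87 for 15% against 40%. In unrounded figures the gain is 2 to 4 points.

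**The case against.** The strongest reply is that no consequence is documented. The plan gives no correlation, effect size, alpha or power target. It says its sample size follows an approval guideline and has no statistical basis, and it puts descriptive percentages first. The exclusions for poor hygiene, rampant caries, xerostomia and severe bruxing remove the patients who would create most of the correlation. With one set per patient the error is conservative, so no false claim of a difference is invited.

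Scores may also sit near the ceiling. The only success rates quoted are for the adhesive, 100% at two years and 98% at three. With an assumed 98/1.5/0.5% distribution, power is 21.0 vs 22.1, 21.3 vs 23.6 and 20.5 vs 23.6 at correlations 0.1, 0.2 and 0.3, so the choice of test hardly matters. Blocking is not free either: with 5% missing restorations it only breaks even at a correlation of about 0.1.

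All of this stands, and it limits the importance of the point. It does not remove the mismatch, which is between a stated design and a stated test and needs no assumption. Nor do the exclusions show that the correlation is zero. The objection that a simple remedy would do is also partly right. With one complete set per patient and tied ordinal scores, a Friedman test came within 0 to 2 points of the blocked rank test (for example 74.0 vs 75.7).

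**Conclusion.** The concern holds. That the tests do not fit the matched design is certain; the size of the loss is not. If most patients have one set, as the stated numbers imply, Kruskal-Wallis is conservative under any positive within-patient correlation. A plausible cost is a few power points, rising to about 10 at correlation 0.3 with scores well below the ceiling, and nil at zero correlation. These figures rest on assumed correlations, shifts and score distributions; only the 45 sets derive from the protocol.

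Inflated false positives would need many two-set patients together with patient-by-material variation, which the documents neither suggest nor exclude. The log-rank issue is secondary. The percentages and Kaplan-Meier curves are unaffected, and no stated power is breached. This should be corrected because correction is cheap, but it ranks at the lower end of the changes worth requiring.

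**What to change.** In Data Analysis, name the patient as the block.

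- **FDI scores at 36 months.** Replace Kruskal-Wallis with a rank test blocked on patient: rank all restorations together, sum a patient's two same-material rank scores where there are two sets, and permute material labels within patient. With one complete set in every patient this is a Friedman-type test.
- **Incomplete sets.** Permute over the materials the patient has, using the mean score per material (doubled for two-set patients). Simulated size with 5% missing was 3.9 to 5.2%.
- **Two-set patients.** Do not rely on Skillings-Mack, or on a patient-stratified test that treats the two same-material restorations as independent. The latter reached a size of 9.1 to 11.0% with 22 of 23 two-set patients.
- **Estimates.** Where counts allow, add odds ratios with 95% CIs from a cumulative-logit GEE or mixed model with patient as cluster, but keep the permutation p-value. A binary GEE Wald test had size 6.4 to 6.9% with 23 patients, and at 95% top scores its odds ratios were not estimable in 26 to 32% of runs.
- **Survival.** Keep the Kaplan-Meier curves and stratify the log-rank test by patient when patients have one set. With many two-set patients, sum the log-rank scores per patient and material and permute them in the same way. With 22 of 23 two-set patients, share 0.3 and 15% failures, the stratified test had size 8.3 to 10.2% and the permuted one 4.0 to 4.3%.

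**Cost.** Analysis wording, patient and set identifiers in the data file, and possibly a routine outside the basic SPSS menus. No new data or patients. If the correlation is truly zero, the blocked rank test gives up 0 to 1 power point with one complete set per patient, 1 to 3 with complete two-set patients, and 2 to 4 with 5% of restorations missing. The stratified log-rank test gives up at most 3, and the permuted version at most 1.

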In vitro wear testing methods are used to measure wear and predict in vivo wear of composites. These methods are reliable and more cost effective than in vivo trials and allow quantitative measurement of wear.^{36,37} From data produced from in vitro wear resistance testing, the 3M Bulk Filled Flowable material has adequate wear resistance to be placed in a class II load bearing area.

Table 1: *In vitro* wear of bulk placed composite resins

Materials	Type	Volume/(mm ³)
Venus Bulk Fill-Flowable/Heraeus Kulzer	Flowable/nano-hybrid	0.024±0.004 ^{A,F}
Filtek Bulk Fill/3M ESPE		0.012±0.001 ^{B,C}

Tetric Evo Ceram BulkFill/Ivoclar	Nano-hybrid	0.011±0.002 ^C
SureFil High Density Posterior Restorative (HDR)/Dentsply	Packable	0.007±0.001 ^D
SureFil SDR Flow/Dentsply	Flowable	0.04±0.01 ^E
Sonic Fill/Kerr	Packable/nano-hybrid/sonically activated delivery	0.02±0.004 ^F
Quixx Posterior Restorative	Packable	0.02±0.006
Z100/3M ESPE/(Control)	Packable/microhybrid	0.004±0.001 ^G

Studies in the past suggest that highly filled microhybrid composites may have greater wear resistance for contact-supporting posterior restorations than flowable microfilled resins.^{39,40} However current generation flowable composites have higher filler content and demonstrate higher wear resistance than early flowable resins and even some conventional bulk filled materials (Table 1).⁴¹⁻⁴³

Experimental Design and Methods:

This clinical trial will compare three techniques using three materials (one for each technique) for restoring class II preparations. The purpose of this clinical trial is to evaluate the effectiveness of a flowable resin composite (Filtek Supreme Ultra Flowable Restorative, filler content: 65 wt% and 46 vol%) used in Class II restorations compared to a conventional highly filled composite resin (Filtek Supreme Ultra, filler content: 72.5 wt% and 55.6 vol%) and Filtek Bulk Fill in class II restorations. This is a randomized prospective single-center, single-blinded, clinical trial 36 months in duration. We propose using one bonding agent (Scotchbond Universal, 3M ESPE) for this study with a total etch technique (the enamel and the dentin are etched). Success with Scotchbond Universal, using the total etch technique was 100% in a 2 year⁴⁴ and 98% a three year⁴⁵ clinical study.

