Each restoration will be evaluated directly and indirectly at baseline (one week after restoration placement), at 6 months, 1, 2 and 3 years. The direct clinical evaluations will be made using a modification of the USPHS and FDI guidelines. Each restoration will be evaluated for proximal contact, marginal discoloration, secondary caries, loss of anatomical form, and marginal adaptation, surface condition and post operative sensitivity. Digital images will be used to document marginal staining and color match of the composite restoration to the tooth. A visual analog scale will be used to evaluate the sensitivity of the restoration by placing a cotton pellet soaked with skin refrigerant for three seconds. The subject will mark their response on a calibrated

line (10mm) where 1 represents no pain and 10 represents the worse pain possible like major surgery, childbirth etc.

Evaluators will be trained and calibrated. Preclinical sessions will train clinicians by preparing and restoring at least two extracted teeth mounted in stone. A clinical training session will train clinicians to conduct the evaluations during sessions using patients with similar restorations placed in a previous clinical trial. Scores for each evaluator will be compared to other evaluators and inter-evaluator comparisons made. The trained evaluators will independently evaluate each restoration in our clinical study and a forced consensus obtained if necessary. Those who evaluate the restorations must not evaluate the restorations they placed. Additional training will also be obtained by the e-calib tool.

Data Analysis:

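### Each FDI criterion is compared at 36 months as if the three materials were in different patients, although each patient receives all three, and no pairwise difference or interval is planned

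*Combined protocol and SAP*

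**What the plan says.** Distribution of Restorations gives each patient one restoration of every material, and allows a second such set where the patient needs it. Number of Restorations plans 50 restorations, expects about 10% loss over 36 months and wants at least 40 at the last recall; the Objective makes clear that the 50 is per material.

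The stated questions are comparisons between materials. Under Experimental Design and Methods the flowable composite is to be "compared to a conventional highly filled composite resin (Filtek Supreme Ultra, filler content: 72.5 wt% and 55.6 vol%) and Filtek Bulk Fill". Materials and Methods likewise says that the incrementally placed materials will be compared with one another and with the bulk fill.

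The Data Analysis section has two tests. One is Kruskal-Wallis, with "p-values) for each FDI criteria at the thirty-six month recall". The other concerns failure: "Restoration survival at thirty-six months will be assessed using Kaplan-Meier survival analysis and Log Rank (Mantel-Cox) test for equality". Neither is described as paired, stratified or clustered by patient. No pairwise contrast, confidence interval, significance level, primary outcome or exploratory label appears in the supplied text.

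The rest is descriptive. Percentages and frequency distributions are reported, "A sample size of 50 restorations is not based on a statistical plan", and the Summary adds "For each category in the evaluation, percentages of alpha (perfect) scores will be tabulated".

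**The concern.** The design is a block design with the patient as block. Hygiene, diet, bite force and caries risk are shared by the three restorations in a mouth, so their scores are likely to be positively correlated. Kruskal-Wallis leaves that shared variation in its error term. A real difference between materials is then harder to detect than the design allows.

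The test also asks only whether the three materials are alike. A small p-value does not say whether the flowable or the bulk fill is the one that differs. Percentages and mean ranks will suggest a direction but carry no measure of uncertainty. A large p-value without an interval cannot separate similar performance from too little information. In a trial whose size was not set by power, a finding of no difference is a likely report, so that distinction matters.

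**Working it through.** **Plan's own figure.** 40/(1 − 0.10) = 44.4, so 45 placed restorations per material would cover the stated loss; 50 is a deliberate margin. The plan gives no power or alpha to reproduce. Expected at 36 months: 50 × 0.90 = 45 per material, taken here as 45 sets with one set per patient.

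**Why Kruskal-Wallis is conservative here.** Rank all 3n scores together. Let S_j be the sum over patients of (rank for material j − that patient's mean rank).
- Kruskal-Wallis: H = [(3n − 1)/n] × ΣS_j² / SS_total, roughly 3ΣS_j² / SS_total.
- Patient-stratified mean-score test: Q = 2ΣS_j² / SS_within patients.
- With no material effect, SS_within is about (2/3)(1 − r) SS_total, where r is the within-patient correlation of the ranks. Hence Q ≈ H/(1 − r).

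At r = 0 the two agree. At r > 0, H is too small by the factor (1 − r).

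**Simulated size and power at an assumed 0.05.** The assumptions are a latent normal score cut at 60/25/10/5%, 45 sets, and a latent shift of 0.5 in one material (perfect scores 60% to 40%). Correlations are on the latent scale.

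| Within-patient correlation | Kruskal-Wallis size | Kruskal-Wallis power | Mean-score power |
|---|---|---|---|
| 0 | 0.05 | 56% | 55% |
| 0.2 | 0.03 | 55% | 63% |
| 0.4 | 0.015 | 55% | 73% |
| 0.6 | 0.005 | 53% | 84% |

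Friedman's test has power 52%, 60%, 71% and 84% in the same four rows. Both set-respecting tests hold a size of about 0.05.

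For rarer outcomes with the same shift, at correlation 0.4: 85/10/5% scores give about 39% against 52%, and a 5% yes/no event gives 23% against 30%.

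**Chance of at least one p < 0.05 when no material differs.** The criteria list (Attachment 2) is not in the supplied text. Eight tests are assumed: survival plus the seven items in the evaluation paragraph ("Each restoration will be evaluated for proximal contact, marginal discoloration, secondary caries, loss of anatomical form, and marginal adaptation, surface condition and post operative sensitivity"). Between-criterion correlation is 0 to 0.5, and survival is approximated as one more criterion.
- Independent tests of exact size: 1 − 0.95^8 = 34%.
- Kruskal-Wallis as planned: 19-23%, 10-15% and 3-8% at within-patient correlation 0.2, 0.4 and 0.6.
- Set-respecting tests, each at 0.05: 23-33%.

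**Log-rank with few failures.** Take three failures, in three patients, all in one material.
- Stratified by patient: each failure occurs among 3 at risk, so chi-square = 2 × 3 = 6 on 2 df and p = exp(−3) = 0.0498.
- Unstratified, 45 per material: expected 45/135 + 44/134 + 43/133 = 0.985. The variance is the sum of e(1 − e) = 0.662. Chi-square = (3 − 0.985)²/0.662 = 6.1 and p = 0.046.

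**Width of the proposed intervals.** Half-width = 1.96 × √[2p(1 − p)(1 − φ)/45], where φ is the correlation of paired perfect/not-perfect scores. At p = 0.60, the bivariate normal gives a probability of both perfect of 0.3902 (latent 0.2) and 0.4574 (latent 0.6).
- φ = (0.3902 − 0.36)/0.24 = 0.126, half-width 18.9 points.
- φ = (0.4574 − 0.36)/0.24 = 0.406, half-width 15.6 points.

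**The case against.** The strongest reply is that the plan is mainly descriptive. It tests no stated hypothesis, makes no superiority or equivalence claim, and takes its 50 from an ADA guideline count. On that view formal error control is not required, and the missing primary outcome and exploratory label are mostly missing detail. This stands. It does not rescue the choice of test or the lack of intervals: a descriptive comparison of materials placed in the same mouth still needs within-patient differences and their uncertainty.

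A reader might infer that one p-value per criterion plus survival pushes the false-positive risk to about a third. The documents do not support that. They state no alpha, the number of criteria is unknown, and the 34% assumes independent tests of exact size. The planned test is conservative, and at correlation 0.6 the overall risk is 3-8%. The set-respecting test raises that risk, so changing the test alone would make an isolated small p-value more likely.

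A reader might also infer that the log-rank test must be stratified for the same reason. No gain was shown. With three failures in one material the stratified version is marginally weaker, and failures should be few if the 98-100% success cited for the adhesive applies.

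Finally, the power gain is largest for the commoner graded scores. For rare events both tests have low power.

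**Conclusion.** The point holds for the FDI criteria. The planned test ignores the patient sets, and no planned contrast or interval answers the comparisons the protocol sets out. The loss is about 8, 18 and 31 percentage points of power at correlations 0.2, 0.4 and 0.6 for the 60/25/10/5% scenario. At 0.4 it is about 13 points for 85/10/5% scores and 7 for a 5% event; at zero correlation there is no loss. The direction follows from the design whenever within-patient correlation is positive. The sizes rest on assumed correlations, score distributions, a 0.5 latent shift, a 0.05 level and one set per patient.

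The finding is loss of sensitivity and unanswered comparisons. It does not establish an inflated false-positive rate or a defective survival test. The change is worth making, with medium confidence in the figures.

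**What to change.** Before unblinded 36-month data are seen:

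1. Replace Kruskal-Wallis with a Cochran-Mantel-Haenszel mean-score test on ranks taken across all restorations, stratified by patient. This also handles two sets per patient. Friedman's test will serve when each patient has one set.
2. For each criterion report three within-patient differences with 95% confidence intervals: flowable against conventional, bulk fill against conventional, and flowable against bulk fill. The percentage of perfect scores, already tabulated, is a suitable scale. Use a score-type interval for paired proportions when events are rare, and keep the patient as the unit where there are two sets.
3. Give the p-values a status. Either label them all exploratory, or let the sponsor name one primary outcome and its alpha, test its three contrasts at that alpha only if the three-group test rejects, and label the rest exploratory. With three groups this gate needs no further adjustment.
4. Keep the log-rank test as planned; stratifying it by patient is optional.

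The cost is analysis wording and a little more analysis work, with no new data or larger sample. The intervals will be wide, about ±16 to 19 points at 60% perfect scores. Nothing is gained if within-patient correlation is near zero. An isolated small p-value becomes more likely than under Kruskal-Wallis, which is why step 3 must accompany step 1.
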